Typhoid fever is an enteric bacterial infection caused by *Salmonella enterica* serovar Typhi (Salmonella Typhi; S. Typhi). It is an important infectious disease in low- and middle-income countries with over 10.9 million new cases worldwide and 116.8 thousand death in 2017. South Asia and Sub Saharan Africa are the most affected areas of the world. Typhoid fever is common in areas with inadequate sanitation and hyegine. In routine practice, diagnosis of typhoid fever is rarely confirmed as diagnostic tests are unavailable or have limited diagnostic accuracy. Blood culture is the commonest reference standard test but has a lower sensitivity. Alternatives to those methods exist but their performance is poor. The Widal test is still used but as it is based on cross-reactive antigens, it lacks sensitivity and specificity. Clinician often use rapid diagnostic tests to diagnose typhoid. A number of typhoid fever RDTs are commercially available but performance data are not available or not consistent from a study to another. This prospective, multicentre, cross-sectional study will be carried out in 3 hospitals of Nairobi, Kenya. 2000 clinically suspected typhoid cases will be enrolled in this study, blood culture as well as serum for RDT will be received. All typhoid positive and equal typhoid negative serum will be tested for investigational RDTs.

This collaborative study between KEMRI and FIND will systematically compare different point of care typhoid tests currently available in the market against the same set of reference standard. The knowledge gained from this trial may benefit health providers' by providing information on diagnostic accuracy of current typhoid test and to decide on utility of these commercial tests. The result obtained from this trial will also be made available to help inform Ministry of Health in Kenya and the WHO Essential Diagnostic list (EDL) and stakeholder decision making more broadly.

LAY SUMMARY

Typhoid fever bacterial disease caused by *Salmonella* Typhi. It is one of the most common serious bacterial diseases in the developing world, with an estimated 10.9 million people contracting the disease worldwide and 116.8 thousand people dying of the disease in 2017. Culture method using blood and bone marrow samples are considered as the benchmark for teting for typhoid disease. Those methods are however time consuming, requires drawing blood from the body, and requires adequate infrastructure and trained staff that are not available in most of areas where the disease is very common locally. There are other methods

but their performance is poor. The Widal test is a cheap test that is widely used despite its high rate of giving test results which wrongly indicates that typhoid is present. Rapid Diagnostic tests (RDTs) have been developed and are available in the market but their performance data are not available or not consistent from one study to another. Therefore, this study will aim to perform a direct comparison of typhoid tests currently in the market to help inform the Ministry of Health in Kenya and the WHO Essential Diagnostic list (EDL) and stakeholder decision making more broadly.

INTRODUCTION/BACKGROUND

Typhoid is an enteric disease caused by the bacterium *Salmonella* Typhi; it is estimated that 11 to 20 million people contract typhoid each year and 128 000 to 161 000 die from the disease; children under 5 are at higher risk of contracting the disease (1).

Typhoid endemic areas are located mainly in South Asia and Sub-Saharan Africa and is transmitted through contaminated water and food (2). The disease is treatable with a specific regimen of antibiotics, however antimicrobial resistance has been reported in several countries, particularly in Pakistan (3). Several vaccines have been developed but their uptake has been low, partly due to limited information on the exact burden of the disease in endemic countries.

The symptoms of typhoid are similar to other undifferentiated febrile illnesses and typhoid can be mistaken with vector borne febrile illnesses such as scrub typhus (4).

Blood and bone marrow cultures are considered the gold standard for the diagnosis of typhoid. Those methods require specific infrastructure and skilled staff that are not always available in LMICs and are not adequate for rapid patient management. In addition, although very specific, blood culture sensitivity is impacted by misuse of antibiotics that lower the bacterial load to undetectable levels in patients' blood (5).

PCR assay for diagnosis of typhoid fever has been used in many studies. Lower concentration for bacterial load in peripheral blood in typhoid fever results in lower sensitivity of PCR (6). Currently there is no validated PCR test in common use, only in-house system which are open to differing interpretation and none would meet the rigors of quality control. (7)

As a consequence, alternatives to blood culture have been used in LMIC. The Widal test is the most used test despite a low performance (sensitivity range: 57-34%; specificity range: 43-83 %;(4) reported in several studies. Other options in typhoid diagnosis are rapid diagnostic tests; among them, three tests (Typhidot, Tubex and Test-itTM Typhoid IgM) have been evaluated in several studies. It has been reported a variability of tests performance in different studies and according to the geographical regions (6). Variability in the test performance reported so far in the literature has hampered WHO to recommend any of these

rapid tests in the EDL. FIND in collaboration with international typhoid experts developed a target product profile outlining the ideal characteristics of point of care tests. As part of this activity it became apparent that no quality data are available that systematically compare all available commercially point of care tests against the same set of reference standards used in multiple populations (e.g. Africa vs Asia). These lack of benchmarking data significantly impedes health providers' ability to decide on the utility of commercial tests in different settings, ultimately restricting use and access. Further the lack of well characterized samples reduces the ability for targeted innovation in the typhoid space.

PROBLEM STATEMENT

Differentiating typhoid infection from other cause of fever in endemic areas is a diagnostic challenge. Although commercial point of care rapid diagnostic tests for enteric fever are available as alternatives to the current reference standard test of blood or bone marrow culture or to the widely used Widal test, their diagnostic accuracy is unclear.

JUSTIFICATION FOR THE STUDY

The gold standard test to confirm typhoid fever is through isolating *Salmonella* Typhi from blood or bone marrow culture. However, this method takes several days to get the test result. In addition, due to misuse of antibiotics and the biology of the pathogens that renders the bacterial load difficult to detect in blood, the blood culture method may give a false negative test result even though the person has typhoid fever. Besides, the blood culture also requires adequate infrastructure and trained manpower that are not easily available in most of endemic areas such as Kenya (5).

A cost-effective alternative to the culture method using blood /bone marrow sample is Widal test which is widely being used in endemic areas. However, published reports show that Widal test has low sensitivity and specificity (10). Other alternatives are Rapd Diagnostic Tests (RDTs) which are easy to use and deliver quick results. There are number of commercially available RDTs for typhoid fever but their performance data are not available or not consistent from a study to another (7). Foundation for Innovative New Diagnostics (FIND) in collaboration with international typhoid experts developed a target product profile outlining the ideal characteristics of point of care tests. As part of this activity it became apparent that no quality data are available that systematically compare all available commercially point of care tests against the same set of reference standards used in multiple populations (e.g. Africa vs Asia). This lack of benchmarking data significantly impedes health provider's ability to decide on the utility of commercial tests in different settings, ultimately restricting use and access. Furthermore, the lack of well characterized samples reduces the ability for targeted innovation in the typhoid space. A second gap that was

identified was the lack of a simple well-performing gold standard suggesting latent class modelling as a solution used for other pathogens with an imperfect gold standard (8).

Therefore, this study will aim to perform a head to head comparison of typhoid tests currently available in the market in two different and geographically distant countries and simultaneously develop a sample set that can be used in future evaluations of emerging technologies and/or to support innovative test development. The knowledge gained from this trial may benefit society by providing information on diagnostic accuracy of currently available point of care typhoid tests. Further the data obtained in this trial will be made available to WHO to support the EDL and stakeholder decision making more broadly.

TRIAL OBJECTIVES AND ENDPOINTS

General Objective

To compare commercially available typhoid point of care tests (RDTs) against a defined reference standard of blood culture and simultaneously develop a sample set to evaluate emerging technologies and/or to support innovation test development.

Primary Objective

- 1.1. To evaluate different RDTs that are commercially available internationally for detecting antigens or antibodies to *Salmonella* Typhi and use Blood culture as standard for comparison.
- 1.2. Establish a biorepository of well characterized specimen collection that can be used to evaluate emerging tests.

Secondary Objectives

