This is a prospective multicentre diagnostic accuracy study using collected blood and/or serum samples that will be conducted in three hospitals at Nairobi, Kenya. Participants will be recruited when they present to three hospitals where the study will take place. Clinical officers appointed in the 3 hospitals will collect blood samples from individuals older than eight years presenting with fever because most documented typhoid fever cases involve school-aged children and young adults. The samples will be transported in cold chain to the Centre for Microbiology Research (CMR), KEMRI laboratories where they will be processed using blood culture. Once culture results are available, investigational RDTs will be performed on all blood culture positive and equal culture of negative serum.

Trial Population

The trial population will be composed of adults and children suspected of typhoid between 8-65 years of age because most documented typhoid fever cases involve school-aged children and young adults. Participants will be recruited in 3 hospitals in Nairobi, Kenya.

Inclusion Criteria

Participants are eligible to be included in the Trial only if all of the following inclusion criteria apply:

- Individuals aged 8 years of age to 65 years of age
- History of fever or axillary temperature of >37.5^oCfor at least 3 consecutive days within the last 7 days prior to enrolment
- Clinical suspicion of enteric fever
- One of the following scenarios:
 - Presents to outpatient department or Emergency Department
 - Admitted to hospital within last 12 hours
- Able and willing to provide informed consent (and assent when required)

Exclusion Criteria

Participants are excluded from the Trial if any of the following exclusion criteria apply:

- Unwillingness to participate in the study
- Inability to provide the required volume of blood
- Unwillingness to provide blood
- Known non-infectious / Non typhoid Infectious causes of fever or other alternate diagnosis of fever

Screen Failures

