The reported values for prevalence of Salmonella Typhi positive patients in Kenya is 5% (Data from personal communication with [name] Co-PI). The reported values of sensitivity and specificity of diagnostic tests are generally low, (Review article on typhoid RDTs summarizes TUBEX test from IDL Biotech has sensitivity of 78% and specificity of 87%, TestTM It from LifeAssay has sensitivity of 69% and specificity of 90%, Typhidot from Reszon Diagnostic has sensitivity of 78% and specificity of 77%.(9) Similarly reported sensitivity and specificity of SD Bioline Salmonella Typhi IgG/IgM from Abbot and Typhoid IgG/IgM Combo rapid test from CTK Biotech are 69%/76% and 40-79%/68-79% respectively (15)). For the purpose of determining the sample size, sensitivity and specificity were both assumed to be 50%, which corresponds to the scenario that requires the highest number of samples to estimate sensitivity and specificity. Based on this hypothesis, and on the feasibility of recruitment at the sites of enrolment, it was decided to set the sample size in order to recruit at least 100 culture positive and culture negative samples in Kenya. These sample sizes will allow to estimate the sensitivity of the test with 80% power to detect a 95% confidence interval of width of +/- 14% in Kenya (11). Based on the prevalence mentioned above, this number of positive samples requires the enrolment of at least 2,000 participants in Kenya (at a prevalence of 5%). From a similar study carried out by an MSc student in our lab that we supervised (Performance of tubex® tf IGM antibody test against culture in typhoid fever detection in Nairobi county, MSc Thesis by [name], JKUAT, 2019), the average number of patients presenting with febrile illnesses at Mbagathi County Hospital was 20 per day, using this as a basis and considering their relatively smaller sizes, we estimate that for Medical Missionaries of Mary, Reuben Centre Hospital and City Council Clinic, we will have 10 and 5 patients presenting per day in Medical Missionaries of Mary, Reuben Centre Hospital and City Council Clinic respectively. We plan to sample for only 3 days in a week (Mon-Wed) due to the observed trend of high patient inflow on these days from [name]

[name]'s MSc work (total 35 patients per day, 420 per month). This works out to a minimum of 2,520 which is above the sample size of 2,000 participants that we are targeting.

TRIAL PROCEDURES

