All samples preparations (blood culture and serum preparation) will be conducted in parallel. Blood culture will be done using an automated blood culture system (BD BACTEC 9050). BACTEC vials will be processed as per manufacturer's instructions. Bottles will be incubated until signal-positive or till the end of day 5, whichever is earlier. When positive signal is observed, bottles are unloaded from instrument and Gram's stain and cultures and biochemical tests to identify *Salmonella* Typhi will be performed using standard microbiological procedures. Patients will be classified as typhoid or non-typhoid cases according to the blood culture results. However, since the results of the blood culture may take several days to be available, serum will be separated from all whole blood samples and will be aliquoted. It is expected that at least 100 blood culture positive and 100 blood culture negative samples will be tested with index tests and will be kept for long term storage.

Testing with the index tests will be performed in batch at the end of each month while the remaining volumes of the selected sera will be kept at -80°C. Depending on the initial volume that will differ between adult and children samples, 3 to 6 aliquots will be kept at -80°C for long term storage and will be used for future evaluation of diagnostic tests.

Investigational products

Reference standard tests to identify Salmonella Typhi:

All blood samples collected from study participants will undergo blood culture.

• Blood culture: Blood culture is considered as gold standard for the diagnosis of typhoid fever. Blood culture is a routine process for diagnosis of typhoid fever.

Index tests:

Index tests are RDTs that will be performed according to manufacturer's instructions by trained laboratory personnel. The readers of the index tests and reference standard test will be blinded to the results of the other tests.

Typhoid RDTs for inclusion in the study were selected by the study team based on a combination of the following criteria:

- RDT is CE-marked
- Published independent evaluation data
- International availability
- Volume of samples
- Price of the test
- Turnaround time

RDTs will be procured by FIND and shipped to the study sites in Kenya. There are no financial ties of any nature with the manufacutrers. All selected RDTs which will be included in the study are shown in Table 2.

Table: 2 Lists of RDTs

1	SD Bioline Salmonella Typhi IgG/IgM Fast

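### Testing only as many negative sera as there are positives lets a shortfall in positives take the negatives below the planned 100; state a floor of 100 negatives

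*Combined protocol and SAP*

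**What the plan says.** Two places in the protocol give the testing rule, and both tie the negatives to the positives. The opening summary has "All typhoid positive and equal typhoid negative serum will be tested for investigational RDTs". Study Design says that, once culture results are known, "investigational RDTs will be performed on all blood culture positive and equal culture of negative serum".

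Two other places give a number. Under Sample Size, "it was decided to set the sample size in order to recruit at least 100 culture positive and culture negative samples in Kenya"; enrolment of at least 2,000 is derived from this at 5% prevalence, a figure taken from personal communication. Under Study workflow, "It is expected that at least 100 blood culture positive and 100 blood culture negative samples will be tested with index tests".

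On the supply of negatives, Study workflow says that, because culture takes several days, "serum will be separated from all whole blood samples and will be aliquoted". Index tests are run in a batch at the end of each month, and storage at -80°C is described for the remaining volume of the sera that were selected. The budget justification archives 100 positives and the same number of negatives.

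No section says which rule governs if positives fall below 100, or how the negatives are chosen.

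**The concern.** Specificity is half of primary endpoint 1.1. Its precision depends on the number of negatives tested, and negatives are not scarce: at 5% prevalence about 95% of participants are expected to be culture-negative. A shortage of positives unavoidably costs precision for sensitivity. Only the equal-number rule passes that shortage on to specificity. Because the enrolment target has no margin, the two rules could easily diverge in practice, and the laboratory would have no instruction on which to follow.

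**Working it through.** **Inputs.** Target 100 per group, prevalence 5%, enrolment at least 2,000, planning value 50% for sensitivity and specificity, ±14 points with 80% power, and an estimate of 2,520 patients presenting (all from Sample Size). Wilson 95% intervals (Statistical Analysis Plan section). Eleven index tests (Table 2). Six collection months (Table 7). Prevalences of 4% and 3% are assumptions made here; the documents give only 5%.

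**1. The plan's own figures.** n = (1.960 + 0.842)² × 0.5 × 0.5 / 0.14² = 100.1, which matches the stated 100. Enrolment = 100 / 0.05 = 2,000. Both sums are right; the difficulty lies in the testing rule.

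**2. Chance of a shortfall.** Take positives as Binomial(N, prevalence). Under the equal rule, the chance of fewer than 100 positives is also the chance of fewer than 100 negatives tested.

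| Enrolled | Prevalence | Expected positives | P(fewer than 100) |
|---|---|---|---|
| 2,000 | 5% | 100 | 48.6% |
| 2,200 | 5% | 110 | 15% |
| 2,520 | 5% | 126 | 0.6% |
| 2,000 | 4% (assumed) | 80 | 98.5% |
| 2,000 | 3% (assumed) | 60 | above 99.9% |

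At 2,000 and 5%, the central 95% range of positives is 81 to 120. Given a shortfall, the mean count is 92.

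**3. Effect on specificity.** Wilson half-width = z√[p(1−p)/n + z²/(4n²)] / (1 + z²/n), with z = 1.960. For n = 100 and p = 0.5: 1.960 × √(0.0025 + 0.000096) / 1.0384 = 0.096, or 9.6 points. The 87% column uses one of the specificities quoted under Sample Size.

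| Negatives tested | Half-width at 50% | Half-width at 87% |
|---|---|---|
| 100 | 9.6 | 6.6 |
| 92 (mean when short, 5%) | 10.0 | 6.9 |
| 81 (lower 95% limit, 5%) | 10.6 | 7.3 |
| 80 (expected at 4%) | 10.7 | 7.4 |
| 60 (expected at 3%) | 12.3 | 8.5 |

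At the documents' prevalence, the typical loss is 10.0 − 9.6 = 0.4 points, and 1.0 point at the lower 95% limit.

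**4. Extra testing under a floor of 100.** In a shortfall, the additional negatives compared with the equal rule are 100 − 92 = 8 on average at 5%, 100 − 80 = 20 at 4% and 100 − 60 = 40 at 3%. With 11 index tests each, that is 88, 220 and 440 test runs.

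**5. Monthly quota.** 100 / 6 = 16.7, so 17 per month gives 6 × 17 = 102. If each month instead takes the larger of 17 and that month's positives, and about 333 are enrolled per month, the expected total is the sum over six months of E[max(X, 17)] with X ~ Binomial(333, prevalence). This comes to about 111 at 5%, 104 at 4% and 102 at 3%.

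**The case against.** The strongest reply is that a floor already exists. Sample Size speaks of at least 100 of each kind, and the budget justification uses the equal-number wording as shorthand for 100 and 100, so the opening summary and Study Design may mean no more than that. This is a fair reading, and it makes the point largely one of reconciliation. But Study workflow only expects 100 negatives, and nothing makes that figure override the equal rule when positives are fewer.

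The second reply is that enrolment may exceed 2,000. That stands in part: the 49% applies only if enrolment stops there. However, no extension rule is given, the opening summary states 2,000, and the 2,520 counts febrile patients presenting, not eligible and consenting participants.

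Third, equal allocation limits kit use across 11 tests and is a legitimate choice. It does not conflict with a floor set at the number already planned.

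Three stronger readings are tempting and not supported:

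- A reader might infer from the 49% that precision is seriously at risk. Most of that probability is a shortfall of a few sera.
- A reader might infer that a stated precision for specificity is missed. The ±14 points is stated for sensitivity only, and even 60 negatives give a Wilson half-width of 12.3.
- A reader might treat about 1,900 negative sera as a reserve to draw on at the end. That figure assumes 5% prevalence and ignores contaminated cultures and other growth, and long-term storage is described only for the selected sera.

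**Conclusion.** The passages conflict whenever positives fall below 100, and the rule as written does not secure the planned number of negatives. The chance of this is 49% at 2,000 enrolled and 5% prevalence, falling quickly if more are enrolled. The consequence is modest: about 0.4 points of half-width on average when short, and about 1 point at the lower 95% limit. It reaches 2.7 points (12.3 − 9.6) only with about 60 positives, which needs a prevalence near 3% that the documents do not give. The figures assume binomial counts and that every serum tested is analysed; the per-protocol set, which needs results on all tests, can lower the analysed number further. The change is worth making because the loss is avoidable at little cost, not because the primary analysis is in danger.

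**What to change.** In the opening summary and Study Design, replace the equal-number rule with a statement that all culture-positive sera and at least 100 culture-negative sera will be tested, whatever the number of positives. Bring Sample Size and Study workflow into line, so that 100 negatives is a requirement and not an expectation.

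Because index testing is monthly, the final count of positives is unknown when negatives are picked, and unselected sera may not be kept. So prespecify a monthly quota: for example, about 17 negatives per month over the six collection months, or that month's number of positives if larger, drawn at random from that month's culture-negative sera. If collection takes fewer months, the quota must be raised to reach 100.

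The cost is a few sentences, a random selection list each month and, in a shortfall, about 8 more negatives on average through the index tests at 5% prevalence (about 20 at 4%, about 40 at 3%). This is within or close to the 100 already planned. The month-by-month larger-of rule can take the total modestly above 100, to about 111 on average at 5%; if kits are limited, a flat quota of 17 avoids this. No one extra is enrolled. Sensitivity remains limited by the number of positives.
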